- A delay in dosing of more than approximately 7 consecutive days (\pm 2 days), in other words, more than 1 missed dose, due to a dose-related toxicity occurring during the 5-week DLT-assessment period (toxicity that is clearly and directly related to the primary disease or to another aetiology is excluded from this definition).

Isolated elevations of transaminases:

- Grade 3 elevations ($\geq 5 \times$ ULN) in ALT or AST, without concomitant elevation in total bilirubin $> 2 \times$ ULN, that do not return to Grade 1 within 7 days from start of dosing.
- Grade 4 elevations in ALT ($\geq 20 \times$ ULN) of any duration irrespective of total bilirubin.
- Grade 4 elevations in AST ($\geq 20 \times$ ULN) without concomitant elevation in ALT $\geq 20 \times$ ULN or total bilirubin $\geq 2 \times$ ULN that do not return to Grade 1 within 7 days from start of dosing.

Elevations in transaminases with concomitant elevation of bilirubin (Potential Hy's Law [PHL]):

- Elevations in ALT or AST $\geq 3 \times$ ULN with concomitant elevation in total bilirubin $\geq 2 \times$ ULN where bilirubin does not return to meet initial eligibility criteria within 72 hours of onset or 96 hours of start of dosing (-2/+12 hours) whichever is the sooner, and/or ALT or AST do not return to meet initial eligibility criteria within 7 days post start of dose.
- Elevations in ALT or AST $\geq 3 \times$ ULN with concomitant elevation in total bilirubin $\geq 2 \times$ ULN and INR $> 1.5 \times$ ULN (or $> 1.5 \times$ baseline, if elevated at baseline) of any duration.
- Elevations in ALT or AST $\geq 3 \times$ ULN with concomitant elevation in total bilirubin $\geq 2 \times$ ULN of any duration if associated with symptoms or signs of liver impairment (eg, appearance of fatigue, nausea, vomiting, right upper quadrant pain or tenderness, fever, rash, and/or eosinophilia $> 5\%$).

Any of the following haematological toxicities:

- CTCAE Grade 4 neutrophil count decrease lasting > 7 days, despite growth factor support.
- Grade ≥ 3 febrile neutropenia (absolute neutrophil count [ANC] $< 1.0 \times 10^9/L$, fever $> 100.9^{\circ}\text{F}$ [or $> 38.3^{\circ}\text{C}$]) of any duration despite supportive care.
- CTCAE Grade 4 thrombocytopenia lasting more than 7 days or Grade ≥ 3 thrombocytopenia, of any duration, associated with \geq Grade 2 bleeding.

- CTCAE Grade 4 anaemia despite transfusion.

Any Tumour Lysis Syndrome meeting the following criteria:

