Grade 3 thrombocytopenia without bleeding	Any	Withhold AZD4573 until Grade ≤ 2 or baseline level. Restart AZD4573 at the same dose level. Continued dosing can be considered at the discretion of the investigator after discussion with the medical monitor.	No action.
Grade 4 thrombocytopenia without bleeding requiring blood or platelet transfusion	1 st occurrence	Withhold AZD4573 until Grade ≤ 2 or baseline level. Restart AZD4573 at the same dose level.	Withhold acalabrutinib until Grade ≤ 2 or baseline level. Restart acalabrutinib at the same dose level.

Table 13 Recommended Dose Modifications for AZD4573 and Acalabrutinib

Event ^a	Occurrence	Action with AZD4573	Action with Acalabrutinib
	2 nd occurrence	Withhold AZD4573 until Grade \leq 2 or baseline level. Restart AZD4573 with 1 level dose reduction. If not recovered to Grade \leq 2 or baseline level discontinue.	Withhold acalabrutinib until Grade \leq 2 or baseline level. Restart acalabrutinib with 1 level dose reduction or discontinue (see Table 12).
	3 rd occurrence	Discontinue AZD4573.	Discontinue acalabrutinib.
Grade 3 or 4 thrombocytopenia with bleeding requiring blood or platelet transfusion	1 st occurrence	Withhold AZD4573 until Grade \leq 2 or baseline level. Restart AZD4573 with 1 level dose reduction. If not recovered to Grade \leq 2 or baseline level discontinue.	Withhold acalabrutinib until Grade \leq 2 or baseline level. Restart acalabrutinib with 1 level dose reduction or discontinue (see Table 12).
	2 nd occurrence	Discontinue AZD4573.	Discontinue acalabrutinib.

^a Adverse reactions are graded using National Cancer Institute CTCAE version 5.0. All grades refer to CTCAE grading except for TLS, which uses the Howard modification of Cairo-Bishop criteria ([Howard et al 2011](#)).

^b In cases where more than 21 days are needed, a decision to continue, modify, or discontinue study treatment will be made on a case-by-case basis in consultation with the principal Investigator and the Medical Monitor.

Abbreviations: ANC = absolute neutrophil count; ASCO = American Society of Clinical Oncology; CTCAE = Common Terminology Criteria for Adverse Events; ESMO = European Society for Medical Oncology; G-CSF = granulocyte-colony-stimulating factor; TLS = tumour lysis syndrome.

Dose modifications for AZD4573 and acalabrutinib for abnormal liver chemistry results are described in [Table 14](#).

Table 14 Recommended Dose Modifications for AZD4573 and Acalabrutinib for Abnormal Liver Chemistry Results

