Event ^a	Action	
	AZD4573	Acalabrutinib
Isolated^b elevations in ALT, AST, or bilirubin		
Grade 1 Isolated ALT/AST \leq 3 \times ULN or Isolated Bilirubin \leq 1.5 \times ULN	Maintain current dose level. Monitor ALT, AST, ALP, and bilirubin at least 1x per week.	Maintain current dose level and schedule. Monitor ALT, AST, ALP, and bilirubin at least 1x per week.

Event ^a	Action	
	AZD4573	Acalabrutinib
Grade 2 Isolated ALT/AST > 3 to $\leq 5 \times$ ULN or Isolated Bilirubin > 1.5- $\leq 3 \times$ ULN	After 7 days if hepatic enzymes resolve to Grade ≤ 1 , rechallenge at same dose level.	Withhold or continue acalabrutinib (at Investigator discretion, after discussion with the Medical Monitor). To prevent disease progression, monitor disease parameters closely. Monitor ALT, AST, ALP, and bilirubin at least 1x per week. After 7 days if hepatic enzymes appear to be improving and acalabrutinib was withheld, restart acalabrutinib at current dose level.
Grade 3 Isolated ALT/AST > 5-20 \times ULN	If recovered to Grade ≤ 1 within 7 days, allow rechallenge at same dose level. If not recovered to baseline level within 7 days, discontinue AZD4573.	Withhold or continue acalabrutinib (at Investigator discretion, after discussion with the Medical Monitor). To prevent disease progression, monitor disease parameters closely.
Grade 3 Isolated Bilirubin > 3-10 \times ULN	If recovered to baseline level within 96 hours (-2/+12 hours) of the start of the infusion allow rechallenge at same dose level. If not, discontinue AZD4573	Monitor ALT, AST, ALP, and bilirubin at least 1x per week. After 7 days if hepatic enzymes appear to be improving and acalabrutinib was withheld, restart acalabrutinib with 1 level dose reduction or discontinue.
Grade 4^c Isolated ALT > 20 \times ULN or Isolated Bilirubin > 10 \times ULN	Discontinue AZD4573.	Discontinue acalabrutinib.
Grade 4 Isolated elevation ($\geq 20 \times$ ULN) in AST without concomitant elevation in ALT $\geq 20 \times$ ULN or concomitant elevation in TBL $\geq 2 \times$ ULN that fails to return to baseline level within 7 days from start of dosing	Discontinue AZD4573.	Discontinue acalabrutinib.

Event ^a	Action	
	AZD4573	Acalabrutinib

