Grade 4^c Isolated AST elevation $\geq 20 \times$ ULN without concomitant elevation in ALT $\geq 20 \times$ ULN or TBL $\geq 2 \times$ ULN	1st occurrence If recovered to Grade ≤ 1 or baseline level within 7 days of the start of the infusion allow rechallenge at same dose level 2nd occurrence If recovered to Grade ≤ 1 or baseline level within 7 days of the start of the infusion allow rechallenge with 1 dose level reduction 3rd occurrence Discontinue AZD4573	Withhold or continue acalabrutinib (at Investigator discretion, after discussion with the Medical Monitor). To prevent disease progression, monitor disease parameters closely. Monitor ALT, AST, ALP, and bilirubin at least 1x per week. After 7 days if hepatic enzymes appear to be improving and acalabrutinib was withheld, restart acalabrutinib at current dose level at the 1st occurrence and with 1 level dose reduction at the 2nd occurrence . Discontinue acalabrutinib at the 3rd occurrence .
Concurrent elevations in ALT, AST, or bilirubin (Please also refer to Appendix E for actions to be taken in the event of PHL)		
ALT or AST $\geq 3 \times$ ULN with TBL $\geq 2 \times$ ULN (Potential Hy's Law) AND INR $\geq 1.5 \times$ ULN (or $\geq 1.5 \times$ baseline if elevated at baseline) of any duration	Discontinue AZD4573.	Discontinue acalabrutinib.
ALT or AST $\geq 3 \times$ ULN with the appearance of fatigue, nausea, vomiting, right upper quadrant pain or tenderness, fever, rash, and/or eosinophilia $> 5\%$	Discontinue AZD4573.	Discontinue acalabrutinib.
ALT or AST $\geq 3 \times$ ULN and TBL $\geq 2 \times$ ULN where TBL does not return to baseline level within 96 hours (-2/+12 hours) from start of dose and/or AST or ALT do not return to baseline level within 7 days from start of dose	Discontinue AZD4573.	Discontinue acalabrutinib.

Event ^a	Action	
	AZD4573	Acalabrutinib
Grade 3 elevation ($\geq 5 \times$ ULN) in ALT or AST with TBL elevation above baseline level or ULN, but $< 2 \times$ ULN that do not return to baseline level within 7 days	Discontinue AZD4573.	Discontinue acalabrutinib.

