15.12.1 Retreatment Criteria

Retreatment is defined as the first dose of study drug after a significant period of intentional pause in study drug treatment (other than missed doses, eg, study treatment put on hold until resolution of COVID-19).

Retreatment criteria (criteria to be met before participant restarts study drug infusions [and capsules, as applicable]):

All participants:

- 1 Participant has recovered from all treatment-related non-haematological toxicity to CTCAE Grade ≤ 2 .
- 2 Recovery of neutrophils $\geq 1000/\mu\text{L}$ and platelets $\geq 50,000/\mu\text{L}$.
- 3 Participant has recovered from all hepatic toxicity events within the timeframes described in Table 14 above. If biochemical changes in transaminase(s) and total bilirubin are consistent with the definition of HL, the participant may continue to receive study drug

only if all abnormalities have resolved within the timeframes specified in [Table 14](#) above, there are no symptoms of liver injury and INR has not increased above $1.5 \times$ ULN (or $1.5 \times$ baseline). In these circumstances the participant must be made aware of the unknown potential for liver damage with continued exposure to AZD4573 prior to retreatment. Documentation of continued consent is required.

- 4 Recovery of uric acid to $<$ ULN.
- 5 Recovery of changes in uric acid, potassium, phosphorus, creatinine or calcium, or symptoms suggestive of TLS as defined in [Table 13](#).
- 6 In case of any new deterioration in laboratory values, not fulfilling eligibility criteria and deemed as clinically significant by the Investigator, the Medical Monitor must be contacted to discuss whether AZD4573 dosing can be continued.

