If bilirubin fails to resolve within 96 hours (-2/+12 hours) or transaminases fail to resolve within 7 days, or if the event is associated with significant clotting abnormality or clinical symptoms of liver disease, study treatment must be permanently discontinued (the participant remains on study for the 30-day SFU and long-term follow-up [LTFU] visits), and the event must be immediately communicated to AstraZeneca.

For guidance on treating liver toxicity, please refer to [Table 14](#) of this protocol.

During the course of the study the Investigator will remain vigilant for increases in liver biochemistry. The Investigator is responsible for determining whether a participant meets PHL criteria at any point during the study.

Please refer to [Appendix E](#) for the process to be followed to identify and appropriately report cases of PHL. It is not intended to be a comprehensive guide to the management of elevated liver biochemistries.

The Investigator will participate, together with the Medical Monitor, in review and assessment of PHL events to agree whether HL criteria are met. HL criteria are met if there is no alternative explanation for the elevations in liver biochemistry.

The Investigator is responsible for recording data pertaining to PHL/HL cases and for reporting AEs and SAEs according to the outcome of the review and assessment in line with standard safety reporting processes.

Regarding the hepatic toxicity events encountered to date with AZD4573, it has been observed that while the biochemical changes of increased transaminase with concomitant elevation in bilirubin seen in some participants could be classified as HL by its strict definition, they do not follow a pattern that is consistent with true HL predictive of hepatic injury, and are therefore 'PHL' cases. The events are rapidly resolved and to date have not led to any clinical sequelae or lasting hepatic injury. Repeated dosing with AZD4573 following these events has demonstrated that there is no consistent pattern of recurrence and no consistent increase in severity of the events if they do recur.

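### Table 14 both permits AZD4573 rechallenge and orders its discontinuation when isolated Grade 3 ALT/AST, or a first or second isolated Grade 4 AST, has fallen to Grade 1 or below but not to baseline by Day 7

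*Protocol*

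**What the plan says.** Two events in Table 14 of Protocol section 15.12 matter here.

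- **Isolated Grade 3 ALT/AST.** The AZD4573 cell first deals with recovery to Grade 1 or below: "within 7 days, allow rechallenge at same dose level". The next sentence of the same cell reads: "If not recovered to baseline level within 7 days, discontinue AZD4573".
- **Isolated Grade 4 AST** (ALT below 20 x ULN, total bilirubin below 2 x ULN). One row covers an AST "that fails to return to baseline level within 7 days from start of dosing" and discontinues AZD4573 and acalabrutinib. The following row describes the same elevation. At the first occurrence it accepts recovery to Grade 1 or below "or baseline level within 7 days of the start of the infusion allow rechallenge at same dose level". At the second it accepts the same recovery with a reduction of one dose level. At the third it stops AZD4573. Its acalabrutinib column leaves withholding or continuing to the investigator after discussion with the Medical Monitor. It then instructs a restart after 7 days if enzymes are improving (current dose at the first occurrence, one level lower at the second) and a stop at the third.

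Table 14 defines Grade 1 ALT/AST as up to 3 x ULN. Table 2 in section 5.1 requires ALT/AST below 3 x ULN at entry. The dose-limiting toxicity (DLT) criteria in section 15.3 count both events only if they are elevations "that do not return to Grade 1 within 7 days from start of dosing".

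**The concern.** A restart rule and a stop rule for one event should meet at a single recovery level. Here the restart level is Grade 1 and the stop level is baseline, so a range of values satisfies both. Two sites with identical Day 7 results could act differently, one redosing and the other withdrawing the drug permanently, and each could cite Table 14.

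The matter is not trivial for the participant. Section 2.3.1 lists transaminase increase as an important identified risk of AZD4573, so redosing too early is a safety question. Section 14.1 admits only people with no standard therapy available, so an unnecessary permanent stop also has a cost. In the Grade 4 AST case the stop order reaches acalabrutinib as well.

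**Working it through.** No stated figure has to be reproduced; this is a check of two decision rules.

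**Inputs.** Let B be the participant's baseline and X the ALT or AST value at the 7-day limit, both in multiples of ULN. Grade 1 or below means X <= 3 (Table 14). Entry requires B < 3 (Table 2). I take baseline to be a value that meets the entry limit, and the 7-day clock to run from the same dose in all lines.

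**Rules.**

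- Rechallenge permitted: X <= 3.
- Discontinuation ordered: X > B.
- Both apply: B < X <= 3, a range of width 3 - B.

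Because B < 3, the width is always above 0. With assumed baselines:

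| Baseline B (x ULN) | Range where both apply | Width (x ULN) |
|---|---|---|
| 0.5 | above 0.5, up to 3 | 3 - 0.5 = 2.5 |
| 1.0 | above 1.0, up to 3 | 3 - 1.0 = 2.0 |
| 2.5 | above 2.5, up to 3 | 3 - 2.5 = 0.5 |

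If a value within the normal range counts as recovered whatever the baseline, the lower end of the range cannot fall below 1.0. The width at B = 0.5 is then 3 - 1.0 = 2.0. Outside the range the rules agree: at or below baseline, rechallenge; above 3 x ULN, discontinue.

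**Illustration, Grade 3.** ALT baseline 0.8, peak 8, Day 7 value 2.0. Since 2.0 <= 3, the first sentence permits rechallenge. Since 2.0 > 0.8, the second orders a stop. By the isolated-transaminase criteria in section 15.3 this is not a DLT.

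**Illustration, Grade 4 AST, first occurrence.** AST baseline 0.8, peak 25, Day 7 value 2.0. The first row stops both drugs. The second permits AZD4573 rechallenge at the same dose and lets acalabrutinib continue or restart. Again this is not a DLT by those criteria. At the third occurrence both rows stop both drugs, so there is no conflict.

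**Does another section settle the level?**

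- Section 15.12.1, criterion 3, points back to Table 14's timeframes. Its sentence on Hy's Law-type changes does the same ("only if all abnormalities have resolved within the timeframes specified in" Table 14). Neither names a level for these two events.
- Section 17.1.10.9 makes the stop mandatory ("If bilirubin fails to resolve within 96 hours (-2/+12 hours) or transaminases fail to resolve within 7 days") but does not say what counts as resolved.
- Section 15.3 names Grade 1, but it classifies DLTs and does not govern redosing.
- Section 6.12 requires discussion with the Medical Monitor before dosing resumes, section 17.1.6 requires contact if an event is unresolved at 96 hours, and section 8.2.6 asks that discussions about stopping be documented. None gives a level.

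**The case against.** The strongest reply concerns the Grade 3 cell. Its first sentence only permits and its second directs, so a site that stops AZD4573 breaches nothing. That stands. It makes the cell badly drafted rather than impossible to obey, but the stop reading leaves the Grade 1 permission without any effect. The reply is weaker for Grade 4 AST. There, two separate rows reach opposite actions, and the acalabrutinib column of the second row instructs a restart rather than merely allowing one.

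It is also fair that review by the Medical Monitor, and the documented hepatotoxicity discussion that Table 14's footnote requires before Grade 4 rechallenge, make unreviewed redosing unlikely. The reviewers would still have no stated level to apply.

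A reader might infer more than the documents support, in three ways:

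- **That Grade 1 was intended and words were lost.** Thrombocytopenia rows in Table 13 repeat one level for restart and stop ("or baseline level discontinue"), which invites this. But Table 13 covers other toxicities, and every stop rule in Table 14 that depends on recovery uses baseline, including those for Grade 3 bilirubin and for concurrent elevations. The text does not show which level was meant.
- **That the earlier study shows how often this happens.** Section 13.3 reports isolated Grade 4 AST in 2 of 6 evaluable participants at 12 mg monotherapy. That is the trigger, not the overlap. The elevations lasted less than 4 days, and their Day 7 values relative to baseline are not given.
- **That the concurrent ALT/AST and bilirubin rows clash in the same way.** Their 96-hour and 7-day checks may be successive, and Table 14 refers to Appendix E for such cases, which is not in the text at hand.

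**Conclusion.** The point holds for two events: isolated Grade 3 ALT/AST, and isolated Grade 4 AST at the first and second occurrence. In both, Table 14 gives conflicting AZD4573 instructions whenever the Day 7 value is above baseline and at or below 3 x ULN. In the Grade 4 rows the conflict extends to acalabrutinib. The conclusion rests on the wording as printed, on Table 14's own Grade 1 limit, and on a baseline that meets the entry criterion.

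The practical size is modest. The frequency of the overlap is unknown and section 4.1 records that recruitment has stopped. DLT classification has its own levels, so no estimate or sample size changes. The rule is not obsolete, however. Participants may stay on treatment after the data cut-off. Section 15.7 then refers investigators to the Investigator's Brochure, while section 6.13 still cites this protocol alongside it. An ambiguous permanent-stop rule for liver toxicity is worth correcting when the correction is a few words.

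**What to change.** The sponsor's hepatic safety group should choose one recovery level for these rows and use it in both the rechallenge and the discontinuation wording. Either choice removes the conflict:

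- **Baseline**, which matches the other Table 14 stop rows. The Grade 3 cell and the second Grade 4 AST row would then permit rechallenge only on return to baseline within 7 days.
- **Grade 1 or below**, which matches the DLT criteria and the existing permissions. The stop sentence in the Grade 3 cell and the first Grade 4 AST row would then apply only if Grade 1 is not reached within 7 days. Adding baseline as an alternative is unnecessary, because an eligible baseline below 3 x ULN is already within Table 14's Grade 1 limit.

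In the Grade 4 AST rows the chosen level should apply to both drugs, with the third-occurrence stop left as it is. Section 17.1.10.9 should define resolution of transaminases at the same level. The cost is a wording change in three Table 14 rows and one definition; no new data or analysis is needed.

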ALT and AST $\geq 3 \times$ ULN with concomitant TBL $\geq 2 \times$ ULN, NO increase in INR $\geq 1.5 \times$ ULN (or $1.5 \times$ baseline), and NO fatigue, nausea, vomiting, right upper quadrant pain or tenderness, fever, rash, and/or eosinophilia $> 5\%$	If recovered to Grade ≤ 1 or baseline level within 96 (-2/+12) hours, rechallenge at same dose level ^c	Withhold acalabrutinib until recovered. Once recovered, restart acalabrutinib at same dose.

^a Adverse reactions are graded using National Cancer Institute CTCAE version 5.0. All grades refer to CTCAE grading except for TLS, which uses the Howard modification of Cairo-Bishop criteria (Howard et al 2011).

^b Elevations in ALT or AST are considered isolated if bilirubin remains below Grade 1, and elevations in bilirubin are considered isolated if ALT and AST remain below Grade 1.

^c Participants who are considered for rechallenge in the event of Grade 4 transaminase increases or PHL must discuss possible risk of hepatotoxicity with the treating physician, who will document this discussion and participant agreement for continued treatment in the medical records.

Note: Adequate supportive therapy as per institutional guidelines should be given for all toxicities.

Abbreviations: ALP = alkaline phosphatase; ALT = alanine aminotransferase; AST = aspartate aminotransferase; CTCAE = Common Terminology Criteria for Adverse Events; INR = international normalised ratio; PHL = Potential Hy's Law; TBL = total bilirubin; ULN = upper limit of normal.

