17.1.10.3 Nausea and Vomiting

Nausea and/or vomiting are identified risks for AZD4573 and acalabrutinib. Participants with nausea and/or vomiting during therapy should be managed per institutional guidelines with maximal supportive care and diagnostic evaluations as clinically indicated. Participants experiencing prolonged or severe vomiting should be closely monitored and managed as appropriate if dehydration and/or electrolyte abnormalities are observed. Participants should be made aware of the risk of possible overlapping toxicities of nausea and vomiting while receiving combination study treatments.

Nausea and vomiting are considered important identified risks for AZD4573. Events of nausea and vomiting have been observed in approximately half of all participants dosed with AZD4573 and have occurred at all dose levels tested to date (except 3 mg). Prophylaxis with a 5-HT3 antagonist (eg, ondansetron \pm dexamethasone) has been implemented in the Phase I study (D8230C00001) to help alleviate this toxicity.

Therefore, prophylaxis for nausea and vomiting is recommended as follows: administer dexamethasone 8 mg (IV administration preferable but orally also permitted) plus a 5-HT3 antagonist (e.g. ondansetron initially 8 mg to be taken before treatment, then 8 mg every 12 hours for up to 3 days) as anti-emetics for all participants, approximately 30 to 60 minutes prior to all scheduled AZD4573 infusions. Additional doses of dexamethasone 8 mg may be administered if deemed clinically warranted. In addition, in the event of vomiting, participants should remain fully hydrated with additional fluids. Participants experiencing prolonged or severe nausea and vomiting should be closely monitored and managed as appropriate if dehydration and/or electrolyte abnormalities are observed.

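### Table 14 gives opposite instructions for a participant with raised ALT or AST, a listed symptom and bilirubin below Grade 1

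*Protocol*

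**What the plan says.** Protocol Table 14 (Section 15.12) has two blocks.

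- **Isolated block.** Footnote b sets the entry condition: "Elevations in ALT or AST are considered isolated if bilirubin remains below Grade 1". Symptoms play no part. For Grade 2 ALT/AST the AZD4573 entry begins "After 7 days if hepatic enzymes resolve to Grade" 1 or below, and then rechallenges at the same dose. For Grade 3 ALT/AST, recovery to Grade 1 or below "within 7 days, allow rechallenge at same dose level"; without recovery, AZD4573 stops. For Grade 4 AST that recovers within 7 days, rechallenge is allowed at the first and second occurrence, and both drugs stop at the third. Grade 4 ALT stops both drugs.
- **Concurrent block**, headed "Concurrent elevations in ALT, AST, or bilirubin". One row covers ALT or AST of at least 3 x ULN "with the appearance of fatigue, nausea, vomiting, right upper quadrant pain or tenderness, fever, rash, and/or eosinophilia" above 5%. Its action is to stop AZD4573 and "Discontinue acalabrutinib". It has no recovery or rechallenge branch, no symptom grade, no causality test and no bilirubin value.

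Two other sections use the same idea differently. Section 15.3 makes ALT or AST of at least 3 x ULN with total bilirubin of at least 2 x ULN a DLT "of any duration if associated with symptoms or signs of liver impairment", with the same symptom list as examples. Section 17.1.10.9 covers ALT/AST of at least 3 x ULN and/or bilirubin of at least 2 x ULN, and requires permanent discontinuation if, among other triggers, there are clinical symptoms of liver disease.

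Section 17.1.10.3 reports: "Events of nausea and vomiting have been observed in approximately half of all participants dosed with AZD4573".

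**The concern.** A stopping rule and a rechallenge rule in the same table should not both apply to one participant. Here they can, because one block is entered on bilirubin alone and the other has a row entered on enzymes plus a symptom. Several listed symptoms are non-specific, and nausea and vomiting are common with AZD4573.

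Followed one way, a participant with a reversible enzyme rise and mild nausea loses both drugs. Followed the other way, a participant whom the table says to stop is re-exposed. Sites can reasonably differ, so the count of discontinuations for toxicity, and exposure to both drugs, would partly reflect which row each site read. The question remains live although recruitment has stopped (Section 4.1), because Section 6.13 lets participants who benefit continue treatment under the protocol's guidance.

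**Working it through.** No sample-size or error-rate figure is involved. The check applies each Table 14 row to the same participant: bilirubin below Grade 1, INR normal, nausea of any grade.

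| Enzyme finding | Isolated row, AZD4573 | Symptom row | Conflict for AZD4573? |
|---|---|---|---|
| ALT 4 x ULN (Grade 2), resolves | Rechallenge, same dose | Stop both drugs | Yes |
| ALT 10 x ULN (Grade 3), Grade 1 or below within 7 days | Rechallenge, same dose | Stop both drugs | Yes |
| ALT 10 x ULN, not recovered within 7 days | Stop | Stop both drugs | No |
| AST above 20 x ULN, ALT below 20 x ULN, first or second occurrence, recovers within 7 days | Rechallenge (same dose first, one level lower second) | Stop both drugs | Yes |
| Same, third occurrence | Stop | Stop both drugs | No |
| ALT above 20 x ULN | Stop | Stop both drugs | No |

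In the three conflicting cases, the isolated rows also leave acalabrutinib open to continuation or restart, while the symptom row stops it.

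**Does the heading separate the cases?** The concurrent block has five rows. The other four each name total bilirubin: three at 2 x ULN or more, and one at a rise above baseline or ULN but below 2 x ULN. The symptom row alone names none. If the heading is meant to supply a bilirubin condition, the threshold is missing, because the neighbouring rows use two different ones.

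**Do other passages settle it?** They point in different directions.

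- Section 15.3 attaches the symptom list to bilirubin of at least 2 x ULN.
- The last Table 14 row allows rechallenge when ALT and AST are at least 3 x ULN, bilirubin is at least 2 x ULN and none of these symptoms is present. Its natural counterpart would be a stop row with the same bilirubin condition plus symptoms.
- Section 17.1.10.9 stops treatment for symptoms after an enzyme rise with or without raised bilirubin, but the symptoms must be those of liver disease. That is narrower than any nausea, fatigue or fever.

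The first two suggest that a bilirubin condition is meant; the third suggests that it is not.

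**How common is the overlap?** Two figures bear on it. Nausea and vomiting were observed in about half of participants. Section 13.3 reports Grade 4 AST elevations in 2 of 6 DLT-evaluable participants at 12 mg in the first-in-human study (2/6 = 33%, a very small sample), described as isolated, lasting less than 4 days and without clinical signs of significant hepatic dysfunction. The protocol does not give the rate of ALT or AST at or above 3 x ULN, nor how often nausea or another listed symptom coincides with such a rise. The size of the overlap therefore cannot be derived.

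**The case against.** The strongest reply is that the table already separates the cases: a participant with bilirubin below Grade 1 is isolated by footnote b, and a reader who respects the headings never reaches the symptom row. That is a possible reading, but the row does not state it, it leaves the bilirubin threshold undefined, and it sits badly with Section 17.1.10.9. Appendix E, to which the heading refers, is not in the text reviewed and might help.

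Other points stand and limit the concern. A DLT definition and a discontinuation rule serve different purposes and need not share thresholds, so the difference from Section 15.3 is not an error in itself. The table is titled as recommendations, Section 17.1.10.9 requires the cause of raised liver tests to be investigated, and Section 8.2.6 asks that discontinuation discussions be documented.

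Some stronger readings are tempting but unsupported:

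- **That every isolated row conflicts.** Grade 4 ALT, unrecovered Grade 3 and third-occurrence Grade 4 AST do not conflict for AZD4573.
- **That responders drop out of the response analysis.** Section 17.4.2 keeps scanning participants who stop for reasons other than progression, on the same schedule, until documented progression.
- **That half of those reaching 3 x ULN meet both rules.** The figure of about half counts nausea and vomiting at any time, not with a liver event. Section 17.1.10.3 also recommends anti-emetic prophylaxis before every infusion, and some enzyme rises fall outside the conflict.
- **That the listed symptoms are drug effects unrelated to the liver.** The protocol does not say so. It names nausea and vomiting as identified risks and pyrexia as an event of special interest (Sections 2.3.1 and 8.2.11), but Section 17.1.10.9 suggests an acute phase response in participants with signs of liver injury.

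**Conclusion.** The contradiction is real and specific. For a participant with bilirubin below Grade 1 and one listed symptom, the symptom row stops both drugs, while the isolated rows allow AZD4573 rechallenge in Grade 2, recovering Grade 3, and first or second recovering Grade 4 AST elevations. No precedence rule appears in the text reviewed, and the heading does not cure the gap.

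The overlap is unlikely to be rare, given how often nausea and vomiting occur, but no percentage or participant count can be supported. What depends on the reading is discontinuation for toxicity and exposure to both drugs; loss of response data does not follow. The conclusion rests on taking the row and footnote b as written, and on Appendix E containing no rule that orders the two blocks.

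**What to change.** Reconcile the symptom row, its block heading, footnote b, Section 15.3 and Section 17.1.10.9 so that only one instruction can apply to a given participant. The revised text should state:

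- whether the symptom row carries a bilirubin condition and, if so, which threshold;
- whether a participant with a listed symptom can still count as isolated under footnote b;
- whether the symptoms must be judged liver-related, as Section 17.1.10.9 implies, or whether any occurrence suffices.

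Which rule is clinically right is for the sponsor to decide. The cost is the wording of one row and one footnote, with matching text in the two sections. No new data or assessments are needed.
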